		deemed necessary by the investigator, patients may also be observed after subsequent injections.			 Administration Medications for patients treated with daratumumab Lenalidomide 10 mg PO: Days 1 to 28 (continuously) of each 28-day cycle until confirmed PD, unacceptable toxicity, or until end of study treatment. If a patient experiences toxicity to lenalidomide, dose and/or schedule may be modified per institutional standard. After 3 cycles of maintenance therapy, if well tolerated, the lenalidomide dose may be increased to 15 mg daily, at the discretion of the investigator. The start of each cycle may occur ±3 days of the schedule day to accommodate the schedule of the site or patient. Day 1 of subsequent cycles should be adjusted accordingly to maintain the intended cycle duration. Any delays ≥4 days of the schedule day will need to be discussed with the sponsor.

				STUDY PHA	SES/VISI	TS ^a	
	PROCEDURE		SCREENING	Maintenance (Cycles 1–36)	ЕОТ	Follow-up (from the date of last study treatment until the end of study)	NOTES
	PROs						
	EORTC QLQ-C30, EORT EQ-5D-5L	At C1D1, and at the end of 6, 12, 24, and 36 months of treatment, (ie, C1D1, C7D1, C13D1, C25D1 and EOT). PROs should be administered at specified timepoints even after patient discontinues the study treatment.		PROs must be completed prior to conducting any other study-specific procedures. PROs should be completed at EOT if the patient discontinues early.			
	DISEASE EVALUATIONS						
	LABORATORY EVALUATION	S (TESTS TO BE CONDUC	TED AT THE CEN	TRAL LABORATORY)			
	IMWG Response Evaluat Assessment	ion per Investigator	х	D1 of every 3 rd cycle (ie, every 3 months) beginning with C1D1, during the first Year (ie, C1D1, C3D1, C6D1, C9D1, C12D1), followed by every 6 th cycle (ie, C18D1, C24D1, C30D1, C36D1) during Year 2 and Year 3	х	Every 6 months	IWMG Response Assessments during the Follow-up visits will be done for participants who have completed study treatment (36 cycles) or who have prematurely discontinued study treatment (due to reasons other than progressive disease). These assessments are to be performed based on local efficacy laboratory results. Assessments can stop after confirmation of Progressive Disease by the investigator. Determination of progressive disease, as well as other response assessments are to follow the IMWG criteria for assessment of progressive disease and disease response, as outlined in Table 7.
	β2-microglobulin and LDI	Н	X	-	Х	-	-

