1.2. Trial Design

This is a Phase 3, randomized, open-label, active-controlled, multicenter study to be conducted at sites in the United States (US) and Canada to primarily evaluate the conversion rate to MRD negativity following 12 months of maintenance treatment with SC daratumumab in combination with lenalidomide relative to treatment with lenalidomide alone in patients with newly diagnosed multiple myeloma who have received at least 4 cycles of induction with or without consolidation, have undergone HDT and ASCT within 12 months of the start of induction, are within 6 months of the ASCT date at the time of randomization, have very good partial response or better at the time of randomization, are MRD positive at the time of screening, and are anti-CD38 treatment naïve.

The study includes a Screening Period; a Maintenance Phase; an End of Treatment (EOT) Visit; and a Follow-up Phase as described below.

- Screening Period: Screening is to be conducted within 60 days prior to randomization; randomization must be within 6 months of the transplant date. Patients must have undergone HDT and ASCT within 12 months of the start of induction therapy.
- Maintenance Phase: Comprised of up to thirty-six, 28-day cycles. Patients will be randomized to receive maintenance treatment with SC daratumumab in combination with lenalidomide or lenalidomide alone. Study treatment will continue until confirmed progressive disease (PD), unacceptable toxicity, withdrawal from study or the end of study maintenance phase.
- EOT Visit: An EOT visit is to be scheduled 30 days (\pm 7 days) after the last dose of study treatment(s) or, if a patient begins new therapy for multiple myeloma, as soon as possible prior to the start of next-line therapy.
- Follow-up Phase: After the EOT visit, patients will continue to be followed until the end of the study. The end of the study is defined as 36 months from the date of randomization of the last patient. If a patient has died, the date and cause of death will be collected and documented in the eCRF.

Planned enrollment includes a total of 214 patients to be randomly allocated in a 1:1 ratio to one of the two treatment arms, with randomization stratified by cytogenetic risk at screening as determined by the investigator (high risk versus standard/unknown risk).

Study evaluations will include evaluation of the following:

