7. FUNCTIONAL STATUS AND WELL-BEING

7.1.1. Definition

Functional status and well-being will be assessed using three patient-reported outcomes (PROs) measure: the EORTC-QLQ-C30, EORTC-QLQ-MY20, and the EQ-5D-5L, which will be measured at baseline, 6 months, 12 months, 24 months, and 36 months. They will be scored based on the instrument developer guidelines. No imputation will be done for the PRO data.

The EORTC QLQ-C30 includes 30 items resulting in 5 functional scales (physical functioning, role functioning, emotional functioning, cognitive functioning, and social functioning), 1 Global Health Status scale (GHS), 3 symptom scales (fatigue, nausea and vomiting, and pain), and 6 single items (dyspnea, insomnia, appetite loss, constipation, diarrhea, and financial difficulties).

The instrument contains 28 items using a Likert scale with 4 response options: "Not at All," "A Little," "Quite a Bit," and "Very Much" (scored 1 to 4). Two additional items use response options (1 to 7): 1 = Very Poor, to 7 = Excellent. All scale and item scores will be linearly transformed to be in the range from 0 to 100 according to the algorithm in EORTC QLQ-C30 scoring manual, version 3.0 (Fayers et al, 2001). A higher score represents a higher ("better") level of functioning, or a higher ("worse") level of symptoms.

The EORTC Multiple Myeloma Module (QLQ-MY20) has 20-items that make up 4 scales: disease symptoms, side effects of treatment, future perspective, and body image. Scoring and interpretation are similar to the EORTC QLQ-C30.

The EQ-5D-5L is a 5-item questionnaire that assesses 5 domains including mobility, self-care, usual activities, pain/discomfort and anxiety/depression plus a visual analog scale (VAS) rating "health today" with anchors ranging from 0 (worst imaginable health state) to 100 (best imaginable health state). The scores for the 5 separate questions are categorical and cannot be analyzed as cardinal numbers. However, the scores for the 5 dimensions are used to compute a single utility score ranging from zero (0.0) to 1 (1.0) representing the general health status of the individual.

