7.1.2. Analysis Methods

Analysis of PRO data will be performed on the FAS. For subjects with multiple records at the same visit, the closest one to the scheduled visit date will be selected for analysis. Compliance rates for completion of EORTC QLQ-C30, EORTC QLQ-MY20, and EQ-5D-5L at each time point will be generated based on number of received and expected. Compliance is defined as the actual number of assessments received for a visit divided by the expected number of assessments for that visit, the expected number of assessments per visit will be determined by subject-level study completion status.

The PRO endpoints are secondary and not part of the statistical hierarchy. Type 1 error control will not be applied to PRO data.

Key PRO endpoints

- EORTC-QLQ-C30 GHS, Physical Functioning, Fatigue, Pain subscales
- EORTC QLQ-MY20 Disease symptoms scale
- EQ-5D-5L utility score and VAS

Descriptive statistics (n, mean, standard deviation, median, and range) at each time point and the change from baseline will be summarized by treatment group. Line plots of mean change from baseline, with standard error, over time will be displayed by treatment group.

A mixed effects model with repeated measures analysis will be conducted estimating change from baseline at each time point between two treatments. FAS subjects who have a baseline value and at least one post-baseline value are included in the analysis. Change from baseline will be fitted to a mixed effects model including subjects as a random effect, and baseline value, treatment group, time in treatment cycles, treatment-by-time interaction, and randomization stratification factor as fixed effects. A mean change between 5 and 10 points on the 1 to 100 scales of the EORTC QLQ-C30 and EORTC QLQ-MY20 has been defined as noticeable by subjects and regarded as a significant change or a meaningful change (EORTC Quality of Life Group).

For the key PRO endpoints, time to worsening and time to improvement will be derived. A distribution-based method will be used to define improvement/worsening in scores, i.e., half standard deviation away from the mean score at baseline combining both treatment groups.

Time to improvement will be summarized by using descriptive statistics such as mean, standard deviation, median and range.

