Time to worsening will be estimated using Kaplan-Meier methods. The hazard ratio for daratumumab plus lenalidomide relative to lenalidomide and its associated 95% confidence interval (CI) will be calculated based on the stratified Cox proportional hazards model by the stratification factor at randomization. Death due to disease progression will be considered as worsening. Subjects who have not met the definition of worsening will be censored at the last PRO assessment. Subjects without baseline assessment or post-baseline assessment will be censored at date of randomization. A Kaplan-Meier figure for the key PRO endpoints will be generated to show time to worsening and censored subjects.

Other PRO endpoints

Other scales of EORTC QLQ-C30 and QLQ-MY20 include:

- EORTC QLQ-C30
 - functional scales: role, cognitive, emotional, and social
 - symptom scales: nausea and vomiting
 - single-item score: dyspnea, loss of appetite, insomnia, constipation, diarrhea, and financial difficulties
- QLQ-MY20

- side effects of treatment
- future perspective
- body image.

The change from baseline at each time point will be summarized descriptively by treatment group.

REFERENCES

Signature

User	Date	Reason

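### Time to PRO worsening counts deaths from progression without a time limit, so one late death can take the Kaplan-Meier curve to exactly zero

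*SAP*

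**What the plan says.** SAP 7.1.2 plans a Kaplan-Meier figure and a stratified Cox hazard ratio for time to worsening of the key PRO endpoints. These are seven scores: four QLQ-C30 scales, one QLQ-MY20 scale, and the EQ-5D-5L utility and VAS. Worsening is "half standard deviation away from the mean score at baseline combining both treatment groups".

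Three rules set the event and censoring times:

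- The rule for deaths carries no time limit: "Death due to disease progression will be considered as worsening".
- Everyone else without an event, including those who die of another cause, leaves the risk set when their last questionnaire was filled in.
- A separate rule covers people who lack questionnaires: "Subjects without baseline assessment or post-baseline assessment will be censored at date of randomization".

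SAP 7.1.1 gives the schedule: the questionnaires are those "which will be measured at baseline, 6 months, 12 months, 24 months, and 36 months". The PRO row of the protocol's Time and Events Schedule, Part 1, gives the visits as "ie, C1D1, C7D1, C13D1, C25D1 and EOT" and adds: "PROs should be administered at specified timepoints even after patient discontinues the study treatment". The Maintenance Phase is "Comprised of up to thirty-six, 28-day cycles" (SAP 1.2). The same section has date and cause of death collected until the study ends, 36 months after the last randomization. SAP 1.4 plans one year of accrual.

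**The concern.** Take two patients with identical forms, neither of whom has worsened. The one who stays alive leaves the risk set at the last form. The one who later dies of progression stays at risk until death and is then an event. Remaining at risk depends on something that has not yet happened, which Kaplan-Meier and Cox methods do not allow.

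The effect is strongest once PRO collection has ended. From then on everyone still at risk is a future event, so the curve describes deaths in a period when quality of life was no longer measured. A reader of the figure would conclude that nearly all patients worsened when half may not have. The SAP guards against a related problem for PFS: Table 4 censors progression or death that follows two or more consecutive missed evaluations. Time to worsening has no such guard.

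**Working it through.** **1. The plan's own figures.** The SAP states no figure for time to worsening. The simulations use the PFS inputs of SAP 1.4, so those were reproduced first. With exponential PFS, uniform accrual over 12 months and 36 further months, expected events per arm are 107 × [1 − (e^(−36λ) − e^(−48λ))/(12λ)], where λ = ln 2 / median.

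- R (median 60 months, λ = 0.01155): 107 × (1 − 0.616) = 41.1
- DR (median 120 months, λ = 0.00578): 107 × (1 − 0.785) = 23.0
- Total 64.1, against 64 in the plan
- Power: Φ(√64 × ln 2 / 2 − 1.96) = Φ(0.813) = 79.2%, against about 79%

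**2. Timeline.** 36 × 28 = 1,008 days = 33.1 months. Adding 30 days to the EOT visit gives 1,038 days = 34.1 months. Follow-up of the first patients is 12 + 36 = 48 months. Deaths therefore continue to be collected for up to 48 − 34.1 = 13.9 months after the last form, and for 36 − 34.1 = 1.9 months in the last patient randomized.

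**3. Logic.** If k unworsened patients in an arm die of progression after that arm's last form, they are the whole risk set. The estimate is multiplied by (k−1)/k, then (k−2)/(k−1), and so on to 0. This needs k ≥ 1 and no other assumption.

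**4. Example.** Of 107 patients, 50 worsen by month 24, 55 are censored at about month 34, and 2 die of progression at months 40 and 44.

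- Month 24: 57/107 = 0.53
- Month 40: 0.53 × 1/2 = 0.27
- Month 44: 0.27 × 0 = 0

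**5. Simulation by visit.** 107 per arm, forms at 6, 12, 24 and about 34 months, forms continued after treatment stop, cutoff at 48 months. Assumed, because the documents do not say: worsening of 10, 25 or 40% per visit, median post-progression survival of 18, 36 or 60 months, 15% missing forms, and 90% of PFS events being progression.

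| Worsening per visit | P(curve ends at 0), R | P(curve ends at 0), DR | Final value if unworsened progression deaths are censored at the last form |
|---|---|---|---|
| 10% | 0.73–0.95 | 0.61–0.83 | 0.43–0.47 |
| 25% | 0.54–0.84 | 0.46–0.71 | 0.12–0.15 |
| 40% (survival 18 and 60 months) | 0.55–0.62 | 0.52–0.58 | 0.04–0.05 |

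At 10%, the estimate at the last form is 0.45–0.49. In the 40% row the chance of any late death is only 0.23–0.40 in R and 0.15–0.28 in DR, so part of that row is ordinary behaviour of a nearly empty risk set.

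**6. Simulation by monthly rate.** Worsening of 1 or 2% per month and post-progression medians of 24 or 48 months (assumed), with forms continued after treatment stop. The R curve ended at zero in 84–99% of trials, with about 2 to 5 late progression deaths in R and 1 to 2.5 in DR. The hazard ratio differed by 0.01 or less from that under the proposed rule.

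**7. Longer accrual.** SAP version 1.0 is dated 5/8/2019, and Amendment 3 of 24 June 2021 lets Canadian sites join. If enrolment began near the first date and was still open at the second, accrual was at least about 25 months and the first patients are followed for about 25 + 36 = 61 months. The documents do not give the first enrolment date. With 26 months of accrual and cutoff at 62, the chance of ending at zero is 0.93–1.00 (R) and 0.81–0.97 (DR) at 10% worsening per visit, and 0.78–0.95 and 0.63–0.84 at 25%.

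**The case against.** The case for leaving the rule alone has five parts, and much of it stands.

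- **Few patients are involved.** A reader might infer many uncounted deaths by letting forms stop one month after progression. That gives 6.6–11.4 late progression deaths in R and 3.2–6.2 in DR. The protocol asks for forms after treatment stops, and Section 9.4 mentions comparison after progression. On that schedule the same scenarios give 1.6–3.6 and 1.1–2.2. Some post-progression forms may be missed, since Section 9.4 has them completed at the site while follow-up after progression is by telephone. Even so, the larger counts do not follow from the plan.
- **The hazard ratio.** A reader might infer that it is distorted for every scale. It is not. Late deaths fall in very small risk sets and carry little weight. The largest gap in any run was 0.84 against 0.89, in a set that included forms ending at EOT.
- **The median.** At 1% worsening per month the R median is reached in 91–99% of trials under the SAP rule and 0–1% under the proposed rule. At 2% per month it is reached in 95–99% and 82–89%. The median is an artefact mainly when worsening is slow.
- **Patients near death may already have worsened.** Tripling the worsening rate after progression lowers late deaths in R to 0.9–2.8 and the chance of a zero to 0.61–0.95.
- **PRO endpoints are outside the testing hierarchy** (SAP 7.1.2).

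None of this removes the fault. No section of either document caps the rule or stops the curve at the last form.

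**Conclusion.** The rule is wrong as written. One unworsened progression death after an arm's last form is enough to take its curve to exactly zero. Under the planned accrual this is likely but not certain: without such a death, the rule does not bring the curve to zero. A handful of patients per arm or fewer cause it.

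The damage is to the Kaplan-Meier tail, the late time-point estimates and, when fewer than half of patients worsen by the last form, the median. The Cox hazard ratio changes little. The MRD, PFS and mixed-model PRO analyses do not use the rule. The mechanism follows from the text alone. Its frequency rests on assumed worsening rates, post-progression survival and form completion, so the simulated ranges show plausible sizes and are not predictions. The change should be made, but it does not bear on the trial's main conclusions.

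**What to change.** In SAP 7.1.2, replace the sentence on death with a rule such as: *A death due to PD counts as worsening only if it occurs on or before the next scheduled PRO time point (6, 12, 24 or 36 months from C1D1) after the last completed PRO, and not after the 36-month time point. Otherwise the subject is censored at the last PRO assessment.*

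Also state that:

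- an EOT form completed early because treatment stopped is not the final scheduled PRO, whereas the EOT form after 36 cycles (about month 34) is the 36-month form, and no death after it counts;
- the Kaplan-Meier display ends at the 36-month time point;
- one named rule takes precedence for a progression death with no post-baseline PRO, which the present text makes both an event at death and a censoring at randomization.

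A flat limit of 12 months since the last form is too loose: at 10% worsening per visit the final estimate is still 0.06–0.32, against 0.43–0.47 with those deaths censored. Within a visit interval some of the same dependence remains, but it is bounded by the gap between forms.

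The cost is a short SAP edit, a small programming change and a few fewer events.
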